### 5.6.4 Radiation Treatment Side Effects

Possible side effects include swelling of the brain, hair loss, localized skin irritation, low blood counts, fatigue, memory loss, hearing loss, nausea and/or vomiting, loss of appetite, headaches, RT necrosis (death of tissue or skin), and secondary cancer.

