Secondary	To assess radiographic response in newly diagnosed HGG patients treated with standard RT and TMZ in combination with BMX-001 compared to standard RT and TMZ alone.	Proportion of subjects with complete or partial radiographic response.	See Section 16.5.2
Secondary	To characterize the repeated-dose pharmacokinetic profile of BMX-001 when delivered in combination with RT and TMZ in newly diagnosed HGG patients.	Plasma concentrations and calculated pharmacokinetic parameters (maximum concentration, time to reach maximum concentration, area under the curve, half-life, total body clearance, and volume of distribution) will be determined for BMX-001.	See Section 16.5.2
Exploratory	To describe patient-reported outcomes of HRQoL in newly diagnosed HGG patients treated with standard RT and TMZ in combination with BMX-001 compared to standard RT and TMZ alone.	Mean change from baseline at each follow-up assessment for subscales of the following PROs include Functional Assessment of Cancer Therapy-Brain Cancer (FACT-BR) version 4, Functional Assessment of Cancer Therapy- Fatigue (FACIT-Fatigue) subscale, version 4, Functional Assessment of Cancer Therapy- Cognition (FACT-Cog) subscale, Beck depression inventory (BDI-II), revised version, Godin Leisure questionnaire.	See Section 16.5.3

Exploratory	To describe changes in hair loss in newly diagnosed HGG patients treated with standard RT and TMZ in combination with BMX-001 compared to standard RT and TMZ alone.	Subjective investigator and patient assessment, photographs.	See Section 16.5.3
Exploratory	To describe change in white matter integrity in newly diagnosed HGG patients treated with standard RT and TMZ in combination with BMX- 001 compared to standard RT and TMZ alone.	MRI Brain Diffusion Tensor /Susceptibility Imaging (white matter integrity).	See Section 16.5.3

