s These assessments should be completed prior to other study-related evaluations at study visits, if at all possible. CNS Vital Signs®(Phase 1) /NeuroCog BAC App (Phase 2) will be done screening (baseline), and then approximately every 8 weeks when a subject returns for a Standard of Care visit during the Adjuvant Phase.

t. Hopkins Verbal Learning Test-Revised (Forms 1, 2, and 3), Trails Making Test Parts A and B, and Controlled Word Association Test will be performed only at baseline, the standard of care visit before the start of the first cycle of adjuvant temozolomide, and the standard of care visit that is 6 and 12 months from the completion of radiotherapy/chemotherapy. See appendices for appropriate versions of these forms to use.

u Hair loss evaluation includes subjective description and photos.

v Patients will continue to complete visits in the adjuvant cycle for up to the 12 planned cycles, as long as they do not have progression on MRI (even if they stop taking adjuvant TMZ). Cognitive testing will be completed even after progression is noted.

w Collection of Gender, Race, Ethnicity, Education completed, employment, and smoking status to be obtained at screening.

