#### 13.8.7 Hair Integrity and Hair Loss

Subjective assessments of hair loss will be obtained by the treating provider for subjects at screening (baseline), after standard RT and TMZ finishes (within 2 to 4 weeks), and standard of care (SOC) clinic visit (approximately every 8 weeks) during adjuvant TMZ.

The photographs will be taken of the craniotomy scar (surgical incision site) and can be taken at any angle or background approximately 6-48 inches from the scalp. There will be no identifiers on the photographs. Up to 6 photographs may be taken at any one time point. Photographs will not include the subjects entire face (will not include eyes, nose, mouth). The photographs will be taken by the PI or trained staff and may be uploaded to the electronic medical record, kept in a separate electronic research file or on paper. One photo per timepoint will also be uploaded to the sponsor electronic database. Participation in these pictures is optional for the patient and they can decline the picture taking at any time. Hair loss will be subjectively described and evaluated clinically by the providers treating the patient and later by the sponsor. If the patient is bald, the photos and descriptions may be omitted.

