16 EXPLORATORY OBJECTIVE: HAIR LOSS

The second exploratory objectives is to describe changes in hair loss in newly diagnosed HGG patients treated with standard RT and TMZ in combination with BMX-001 compared to standard RT and TMZ alone.

Subjective assessments of hair loss were obtained by the treating provider for subjects at screening (baseline), after standard RT and TMZ finishes (within 2 to 4 weeks), and standard of care (SOC) clinic visit (approximately every 8 weeks) during adjuvant TMZ.

Qualitative assessments of hair loss depicted in longitudinal subject photographs will be conducted and summarized. Changes observed in Arm A will be compared to those observed in Arm B.

The analyses group for this exploratory objective will include all treated patients who have both assessments of their hair at baseline and at one or more follow-up assessments.

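### The waiver of hair photos and descriptions for bald patients is not limited to baldness at screening, so hair loss on study can go unrecorded because it was complete

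*Protocol*

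**What the plan says.** Protocol 13.8.7 sets the schedule: "Subjective assessments of hair loss will be obtained by the treating provider for subjects at screening (baseline), after standard RT and TMZ finishes" (2 to 4 weeks afterwards), and then at standard-of-care visits about every 8 weeks during adjuvant temozolomide. The section ends with the waiver: "If the patient is bald, the photos and descriptions may be omitted". Photographs are taken of the craniotomy scar, and a patient may decline them.

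The footnote on hair in Table 4 (Protocol 13) defines what is collected: "Hair loss evaluation includes subjective description and photos". Protocol Table 2 gives the endpoint as "Subjective investigator and patient assessment, photographs".

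SAP 16 sets the analysis: "Qualitative assessments of hair loss depicted in longitudinal subject photographs will be conducted and summarized", followed by "Changes observed in Arm A will be compared to those observed in Arm B". The analysis group is "all treated patients who have both assessments of their hair at baseline and at one or more follow-up assessments".

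Hair loss is an expected effect of both backbone treatments. Protocol 5.6.3 lists it among temozolomide effects seen in more than 30% of subjects. For radiation, Protocol 5.6.4 says "Possible side effects include swelling of the brain, hair loss, localized skin irritation".

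**The concern.** A rule that excuses assessment because a patient has no hair is harmless when the baldness was there before treatment, since such a patient has nothing to lose. Applied to baldness that develops during or after chemoradiation, the same rule excuses recording of the worst possible outcome. The absence of data then carries information about the outcome, and an analysis of recorded assessments alone will look better than what happened.

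What is at stake is the second Phase 2 exploratory objective, a planned comparison of hair loss between arms. If the arms differ in complete loss, the rule can take the worst cases out of the arm with more of them. The trial is open-label and the waiver is discretionary, so the decision to record rests with staff who know the assigned arm.

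**Working it through.** The documents give no sample size, rate, scale or test for hair loss, so there is no stated figure to reproduce. The check is to follow the rules in order.

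1. **What is collected.** The Table 4 footnote makes the evaluation a description plus photos.
2. **What may be skipped.** The waiver in 13.8.7 covers both items, so when it is used nothing of the provider's evaluation need remain for that visit.
3. **When it may be skipped.** The sentence has no time limit and does not separate pre-existing from treatment-related baldness. It follows a schedule that includes every follow-up visit. That it reaches follow-up visits is an inference from the missing limit; the text does not say so outright.
4. **Whether baldness is recorded instead.** Neither document asks for it.
5. **Who is analysed.** SAP 16 needs a baseline and at least one follow-up assessment, and has no rule for follow-up omitted because of baldness.

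Applied to the possible patients:

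| Patient | What the rules allow | Effect on the comparison |
|---|---|---|
| Bald at screening | No assessments | Not in the group; no change was observable |
| Hair at baseline, bald at some follow-ups | Those visits left blank | Stays in the group; worst visits missing |
| Hair at baseline, bald at every follow-up | All follow-up left blank | Leaves the group |
| Hair at baseline, partial loss | Full assessment | Counted as intended |

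The second and third rows are the problem.

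**Direction.** Let *p* be the true proportion of an arm that is bald at every follow-up, and *q* the fraction of those patients whose follow-up is omitted entirely. The proportion with complete loss among analysed patients is *p*(1 − *q*) / (1 − *pq*).

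- With *q* = 0 this equals *p*, the truth.
- With *q* = 1 it is 0 in both arms, whatever the true rates, so any difference in complete loss disappears.
- For *q* between 0 and 1 it lies below *p*. If *q* is the same in both arms, it still rises with *p*, so the order of the arms is kept.

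Neither *p* nor *q* can be filled in from the documents.

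**Other sources.** SAP 11.2.1 tabulates treatment-emergent events by arm and preferred term, with no exemption for baldness, focused on the period to 2 weeks after radiation. Hair follow-up begins 2 to 4 weeks after chemoradiation, so that table closes about when hair follow-up opens. Collection of events stops 30 days after the last BMX-001 dose (Arm A) or the last chemoradiation (Arm B), under Protocol 14.1. SAP 16 does not draw on these data.

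**The case against.** The strongest reply is that the sentence was meant for patients with no hair to assess from the start. Radiation is focal and the photographs are of the scar, so that reading is plausible. It is written in neither document, though, and sites apply what is written.

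Several other points stand and limit the claim:

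- Omission is permitted, not required, and 13.8.7 also says assessments will be obtained.
- A patient leaves the analysis group only if every follow-up is omitted. One recorded follow-up keeps the patient in.
- New alopecia during chemoradiation can appear by arm in the adverse event tables. Table 2 also names a patient assessment, which the waiver does not mention. But 13.8.7 gives no procedure for collecting that assessment, and SAP 16 uses neither source.
- Photographs are optional in any case. Refusal need not follow hair loss, however, whereas the waiver does so by definition and covers the description too.

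A reader might go further and infer that the rule could reverse the comparison between arms. The documents do not support this. The analysis is a qualitative reading with no formal estimate, and equal use of the waiver keeps the order of the arms, as shown above. Unequal use is conceivable in an open-label trial, but nothing in the documents indicates it.

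A reader might also try to put a number on the loss by applying assumed complete-loss rates to 80 patients per arm. That is not supported either. The figure of more than 30% in Protocol 5.6.3 is for any hair loss on temozolomide, not complete loss. SAP 16 analyses treated patients, and SAP 10.3.2 counts 78 and 71 who received protocol treatment. Such a sum would also assume that every bald patient was omitted at every visit.

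**Conclusion.** The concern holds in a limited form. As written, the rules allow hair outcomes to be missing because they were the worst outcomes: visits can be lost for patients who stay in the analysis group, and whole patients can be lost if every follow-up is omitted. The result can understate hair loss in the arm with more complete loss.

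This rests on reading the waiver as it stands, without a limit to screening, and on sites making use of it. The size of the bias is unknown. The importance is low: the endpoint is exploratory and descriptive, and overall survival, cognition and thrombocytopenia are unaffected. It is worth correcting because the correction is small and the planned comparison would otherwise be hard to interpret.

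**What to change.** **Protocol 13.8.7.** Limit the waiver to patients already bald at screening. For baldness that arises later, require a brief description (complete loss) at that visit, even if no photograph is taken.

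**SAP 16.** Keep in the analysis group those patients who were not bald at baseline but whose follow-up was omitted for baldness. Describe them as complete loss where a data query can recover the reason. Report omitted assessments and their reasons by arm. No hair scale exists, so complete loss should be a recorded description, not a score.

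**Cost.** A few sentences across the two documents and a short data query. Treatment, visits and sample size do not change. SAP 16 describes the assessments in the past tense, so the protocol wording may have little effect on future visits and the SAP change carries most of the value. For visits already completed, some reasons may not be recoverable; those should be reported as unknown.

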#### 13.8.8 Medical and Demographic Information

Medical and demographic information will consist of general demographic information (e.g., race, ethnicity, education, employment, smoking status). Demographic information should be collected at the time of screening. Medical information will be abstracted from medical records and study questionnaires.

#### 13.8.9 Bone Marrow Assessments

Bone marrow function will be assessed by CBC with differential (which includes platelet counts) as described in the table in Section 13 Screening and On-Study Tests and Procedures.

#### 13.8.10 MRI Diffusion Tensor/Susceptibility Imaging

MRI diffusion tensor/susceptibility imaging during Phase 2 involves the application of standard MRI imaging of the brain to evaluate white matter integrity. This will be done before contrast injection on subjects enrolled at clinical centers as indicated by the sponsor in Phase 2. All images will be acquired on state-of-the-art 3T scanners.

Imaging should include T1-weighted 3D imaging before and after single dose contrast agent injection as specified in the standardized brain tumor imaging protocol (BTIP,

https://www.ncbi.nlm.nih.gov/pmc/articles/PMC4588759/, Table 1). T2 and FLAIR imaging should also be performed as specified in this publication.

For susceptibility images, images will be acquired using a multi-echo 3D gradient echo sequence.

TE1	=min
TR	=60 ms
flip angle	= 12º
FOV	= 220x220 mm 
matrix size	= 256x256, 2mm slice thickness with no gaps,
	parallel imaging acceleration factor 2.

For **Siemens** scanners, use the following parameters:

For **GE scanners**, use the following parameters:

TE1	=min
TR	=45 ms
flip angle	= 12º
FOV	= 220x220 mm 
matrix size	= 256x256, 2mm slice thickness with no gaps, parallel imaging acceleration factor 2.

Obtain maximum number of echoes (at least 9). Sites should reconstruct and save both magnitude and unfiltered phase images from this sequence.

Diffusion tensor images will be acquired before contrast injection using a multi-channel head coil (at least 8-channels) and a standard single-shot EPI sequence with a parallel-imaging acceleration factor of 2. The parameters will be as follows: TE = 82 ms, TR = 8 s, FOV = 220x220 mm^2, matrix size = 128x128, slice thickness = 2 mm without gap, b-value = 1000 s/mm^2, 5 non-diffusion weighted images and 25 diffusion encoding directions. 75 slices will be acquired to cover the whole brain.

These images will be obtained three times during the study: on day -5 to 0, after standard RT and TMZ (within 2 to 4 weeks), and 24 weeks after the start of standard RT and TMZ (within 2 to 4 weeks).

Images will be cleaned of identifiers (except for the date of the scan which is needed for analysis), encrypted and transferred to the Duke Imaging center for analysis. Please see the sponsor provided Imaging Manual for specifics.

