# **5 PROTOCOL SYNOPSIS**

### 5.1 Purpose

This is a Phase 1/2 study of BMX-001 in combination with standard radiation therapy (RT) and temozolomide (TMZ) in the treatment of newly diagnosed high grade glioma (HGG) patients. Phase 1 was conducted as a single site study at the Preston Robert Tisch Brain Tumor Center at Duke (PRT-BTC). Phase 2 will be conducted as a multi-center study and will include up to 10 additional sites besides the PRT-BTC at Duke.

## 5.2 Phase 1

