#### 9.1.9 Randomization

Within the Phase 2 portion of this study, patients will be randomized using a 1:1 allocation ratio to receive standard of care treatment consisting of TMZ and RT with BMX-001 (Arm A) or without BMX-

001 (Arm B). A permuted block randomization algorithm stratified by grade (III / IV) and by institution will be used.

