h DTI/Susceptibility Imaging is for clinical centers selected by the sponsor and completed at baseline, during the Adjuvant Phase before the start of the first cycle of adjuvant temozolomide, as well as 6 months (approximately 24 weeks, +/- 2 weeks) after radiotherapy/chemotherapy

i Toxicity assessment will continue to be obtained at every SOC clinic visit during the Adjuvant Phase for a minimum of 30 days after last BMX-001 treatment for subjects receiving BMX-001 or last chemo/RT for subjects not receiving BMX-001, and also followed for any unresolved adverse events considered related to study therapy.

j For BMX-001, this dose will be the loading dose. In Phase 2- Applicable only for patients in Arm A.

k For BMX-001, doses (50% of the loading dose) will be twice a week subcutaneously weeks 1-8. There will only be two doses per week regardless of being a loading or maintenance dose. In Phase 2- Applicable only for patients in Arm A. I For patients in Phase 2 Arm B (standard RT + TMZ without BMX-001), vital sign evaluation will only be required on days of the History and Physical assessment.

m Arm A: Patients will be monitored at drug administration with vital signs and injection site reaction at pre dose, at 5 (+/-2), 15 (+/-3), 30 (+/-5), and 60 (+/-5) minutes post administration on the BMX-001 loading dose. Patients will be monitored at drug administration with vital signs and injection site reaction at pre dose, at 5 (+/-2), 15 (+/-3) and 30 (+/-5) minutes post administration on BMX-001 maintenance injection days. See Section 0.

o Phase 2 only, subjects will be randomized after all eligibility criteria is confirmed.

p For Phase 2: For subjects in Arm A, this column is the day of the BMX-001 Loading Dose. For Subjects in Arm B, these items should occur -5 to 0 days prior to the start of RT. The procedures for this visit should not take place until final eligibility is confirmed and randomization has occurred.

q In Phase 2, subjects randomized to Arm B will NOT have a Week 7 or Week 8 research study visit.

r In Phase 2, subjects randomized to Arm B do not have a Week 1 study visit, although they will be in the clinic for the start of RT and TMZ.

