17.2 METHODS OF ANALYSIS

Assuming normality, analysis of variance or a repeated measures analysis may be used to compare change in Arms A and B. Additional analyses will be sub-divided in terms of WHO grade and histological subtype.

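### The exploratory white-matter comparison omits institution and grade, the randomisation strata; if change differs by centre, its standard error is somewhat too wide and the test conservative

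*Protocol*

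**What the plan says.** **Randomisation.** Protocol 9.1.9: "A permuted block randomization algorithm stratified by grade (III / IV) and by institution will be used". Allocation is 1:1.

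**Where imaging is done.** Protocol 13.8.10: "This will be done before contrast injection on subjects enrolled at clinical centers as indicated by the sponsor in Phase 2". The footnote on this imaging to Table 4 in Section 13 agrees: "DTI/Susceptibility Imaging is for clinical centers selected by the sponsor and completed at baseline". The number of imaging centres is not stated. Section 5.1 sets the upper limit: the trial "will include up to 10 additional sites besides the PRT-BTC at Duke", so at most 11.

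**How images are acquired.** Protocol 13.8.10 requires 3T scanners throughout. Of the susceptibility scan it says: "For susceptibility images, images will be acquired using a multi-echo 3D gradient echo sequence". It then gives one table per vendor, with TR 60 ms (read here as Siemens) and 45 ms (GE). The other listed parameters are the same, and sites are to obtain as many echoes as possible, with a minimum of 9. Diffusion tensor imaging has a single specification: "The parameters will be as follows: TE = 82 ms, TR = 8 s", with one matrix, b-value and number of directions for all sites. The head coil need only have at least 8 channels. Site-specific details are left to a sponsor Imaging Manual.

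**Endpoint and analysis.** The endpoint is mean change from baseline at each follow-up scan (Protocol 16.5.3.3, SAP 17.1). For the comparison, SAP 17.2 says that, given normality, "analysis of variance or a repeated measures analysis may be used to compare change in Arms A and B"; Protocol 16.5.3.3 has the same sentence. Neither names institution, scanner, vendor or grade as a model term. Grade appears only as a way of splitting additional analyses. The objective is the third exploratory one and has no sample size, alpha or power.

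**The concern.** When patients are randomised in blocks within institution, the arms are close to balanced at each centre. Differences between centres then contribute little to the arm difference. An analysis that ignores centre still leaves those differences in its residual variance. The estimate is unaffected, but its standard error is larger than it should be and a real difference is more easily missed.

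Imaging measures invite this problem, because centre, scanner and sequence go together, and the protocol itself sets one vendor difference. The imaged subset is also confined to selected centres, so there is little precision to spare. At stake is the precision of one exploratory comparison, not its validity.

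**Working it through.** **No figure to reproduce.** The documents give no sample size, SD, effect size or power for white matter. The size of the effect has to be shown over a range of assumptions.

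**Step 1: what cancels.** If a scanner adds a constant to every image, follow-up minus baseline removes it, provided the patient stays on that scanner. A simulation (80 patients, 4 centres, offset SD equal to patient SD, 1,500 runs) shows this:

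| Outcome analysed, no centre term | Mean SE / true SE | Type I error (nominal 5%) |
|---|---|---|
| Raw follow-up value | 1.18 | 2.6% |
| Change from baseline | 0.97 | 5.5% |

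The simulation error on a 5% rate is √(0.05 × 0.95 / 1500) ≈ 0.6 points, so the second row shows no distortion. A fixed offset, including one from the TR difference, therefore does not harm the planned endpoint.

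**Step 2: what does not cancel.** Change itself may differ by centre. The possible routes are:

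- scale differences or drift between scanners, or a scanner switch between visits;
- local radiotherapy planning (Protocol 9.1.8.1 leaves the plan to the site, and 9.1.8.4 allows techniques from opposed lateral fields to IMRT and VMAT), given that Section 7.3 names radiotherapy as the cause of white-matter damage;
- scan timing: the Table 4 footnote puts the last scan about 24 weeks after radiotherapy/chemotherapy, whereas 13.8.10 and SAP 17.1 put it 24 weeks after the start. Sites following different texts would scan about six weeks apart, the length of radiotherapy. These passages must be reconciled in any case.

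None of these is quantified in the documents.

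**Step 3: size of the loss.** Let ρ be the share of the variance of the change score that lies between centres, with arms balanced within centre. Assume a two-sided 5% test and an effect that gives the centre-adjusted test 80% power.

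- SE ratio: c = 1/√(1−ρ)
- Type I error: 2 × [1 − Φ(1.96c)]
- Power without the centre term: Φ(1.960 + 0.842 − 1.96c)

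For ρ = 0.20, c = 1/√0.8 = 1.118 and 1.96c = 2.191. Type I error is 2.8%, and power is Φ(2.802 − 2.191) = Φ(0.610) = 72.9%.

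| ρ (assumed) | SE ratio | Type I error | Power without centre term | Loss from 80% (points) |
|---|---|---|---|---|
| 0 | 1.00 | 5.0% | 80.0% | 0 |
| 0.02 | 1.01 | 4.8% | 79.4% | 0.6 |
| 0.05 | 1.03 | 4.4% | 78.5% | 1.5 |
| 0.10 | 1.05 | 3.9% | 76.9% | 3.1 |
| 0.20 | 1.12 | 2.8% | 72.9% | 7.1 |
| 0.30 | 1.20 | 1.9% | 67.7% | 12.3 |

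**Step 4: finite-sample check, including the cost of adjusting.** Simulation with permuted blocks of 4 within centre and 1,500 runs per setting. The simulation error on each power is √(0.78 × 0.22 / 1500) ≈ 1.1 points. Entries are power without v with a fixed centre term.

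| Patients, centres (assumed) | ρ = 0 | ρ = 0.05 | ρ = 0.10 | ρ = 0.20 |
|---|---|---|---|---|
| 40, 2 | 78.9 v 78.7% | 77.2 v 78.0% | 76.9 v 78.3% | 73.3 v 76.5% |
| 40, 8 | 77.7 v 77.7% | 75.7 v 75.7% | 74.4 v 76.1% | 68.6 v 75.8% |
| 80, 4 | 79.7 v 79.7% | 78.4 v 79.1% | 76.8 v 78.9% | 72.9 v 79.1% |
| 120, 6 | 80.3 v 79.9% | 79.5 v 80.3% | 74.9 v 78.4% | 72.3 v 78.7% |
| 120, 11 | 79.0 v 78.9% | 77.7 v 79.4% | 78.3 v 81.7% | 73.7 v 80.6% |

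The gain from adjusting is 0 to 1.7 points at ρ = 0.05, 1.4 to 3.5 at 0.10 and 3.2 to 7.2 at 0.20. Where centre has no effect, the term costs at most 0.4 points, which is within simulation error.

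**The case against.** The strongest reply is that nothing here is shown to go wrong. The endpoint is change, so fixed offsets drop out. Diffusion tensor imaging has one specification at 3T, and images go to a single centre for analysis. The vendor difference shows that an offset is possible, not that change varies by centre. All of this stands, and it is why the loss can only be stated conditionally.

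The model wording is also permissive, and Protocol 16.5.3 allows alternative methods. An institution term is unspecified, not excluded. That stands too, but it leaves the choice of model until the data have been seen, for a factor the trial already randomises by.

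Exact balance within centre is not assured. Blocks are also stratified by grade, and Protocol 13.7.1 stops assessments other than cognitive testing at progression, so the later scans may be unbalanced. To that extent the formula overstates the excess in the standard error, and centre differences can instead enter the estimated arm difference. The same model term deals with both.

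A reader might infer from 13.8.10 that patients may move between scanners. The documents do not support that as a criticism: the Imaging Manual, which may contain a same-scanner rule, is not among them. A new acquisition rule would also come late, since the SAP reports enrolment and treatment in the past tense (Sections 4, 8.4.2 and 10.3.2).

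**Conclusion.** The point holds as a low-severity improvement. The white-matter comparison does not specify the stratification factors although its images come from several centres. If change differs by centre, the unadjusted standard error is somewhat too wide. The loss is about 3 points of power or less for centre shares up to 10% and about 7 points at 20% (3 to 7 in the simulated settings, smallest with two centres). These figures rest on an assumed centre share, subset size, number of centres, 5% two-sided test and 80% reference power.

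Three stronger readings are tempting but unsupported:

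- **The error bars are too wide and power is lost, as a fact.** This needs centre differences in change, for which the documents give no figure, and the plan states no power for this endpoint that could be lost.
- **All white-matter images use different scanner settings.** The vendor split in TR concerns susceptibility only.
- **The analysis risks a false positive.** The direction is the opposite: with arms balanced within centre, the test is conservative.

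**What to change.** In SAP 17.2, state that the white-matter model, for both diffusion tensor and susceptibility measures, includes institution (as a random effect if centres are small) and WHO grade as used for randomisation.

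Keep the site or scanner ID from the image headers. This needs saying, because 13.8.10 has identifiers other than the scan date removed and Protocol 17.4 says only that imaging location may be retained. Flag any patient whose scanner or sequence changed between visits, and repeat the comparison without those patients as a sensitivity analysis.

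The cost is one or two SAP sentences and one data field. The statistical downside is a few degrees of freedom if many centres contribute few scans, which a random effect limits. SAP 18 describes a review before the database closes, so the model can be fixed before that point.
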